***PI must attest to the following.***

**\* Process is adequately described to ensure that all persons assisting with the trial are adequately informed about the protocol, the investigational product(s), and their trial-related duties and functions.**

## **8. Subjects - Populations**

### **Inclusion Criteria**

Patients must have: advanced dementia (any form of dementia, including Alzheimer's, vascular, mixed), based on Global Deterioration Score (GDS) > or equal to 6; impairment in at least one ADL (which is inherent in this level of GDS); a physician who is primarily responsible for their dementia-related care whose clinical outpatient site is associated with one of the four Mount Sinai sites in Manhattan; an informal/ unpaid caregiver willing to enroll; a residence in Manhattan where they are currently living (not in a long-term care facility); capacity to consent or a legal representative available to provide consent; conversant in English or Spanish, or their legal representative must be conversant in English or Spanish. We will only enroll adults over the age of 18 - dementia does not occur in patients below the age of 18 and our team is not trained to manage the needs of pediatric patients. Most of our subjects either live with their caregiver or have a home health aide who administers the care. In either case, we will only enroll subjects where they have consistent access to the internet and a device on which they can download video visit software. We will follow the rules outlined by the Office for Civil Rights which guide the type of software that can be used during the COVID-19 pandemic.

**Caregivers:** the caregiver will be the relative or unpaid nonrelative who provided the most hours of help with activities of daily living or instrumental activities of daily living in the prior week; they must be over the age of 18; conversant in English or Spanish

### **Exclusion Criteria**

Exclusion criteria are: patient receiving hospice care or enrolled in another study of a patient/caregiver intervention.

There are no specific exclusion criteria for caregivers where they meet the inclusion criteria above.

**Enrollment Restrictions Based**      No

**Upon Gender, Pregnancy, Childbearing Potential, or Race**

**Age Range(s)**      18 to 64 Years, 65 Years and Over

**Targeted Population(s)**      Adults - Patients , Impaired Mental Capacity, Decisionally Impaired

### **Other Aspects that Could Increase Subjects Vulnerability**

The clinical team caring for the patients in this study have extensive experience of caring for patients with advanced dementia, and are well aware that procedures carried out in routine clinical care may incur greater burden and distress for individuals with moderate-severe dementia. The procedures involved in this study for the patients do not differ from those which would be provided by any in-home clinical service designed to improve the clinical care of patients with dementia.

### **Safeguards to protect Subjects rights and welfare**

We have undertaken numerous steps to protect patients' rights and safeguard their welfare, in light of their likely impaired capacity.

1. The patient's healthcare provider will introduce the study and determine interest before we approach the patient and caregiver.
2. We will ask the patient's healthcare provider to complete a capacity assessment. Where the patient lacks capacity to consent to study involvement (which we anticipate in most cases) we will follow standard protocol for consent in patients lacking capacity (i.e., their LAR will provide authorization)
3. We will clearly state the dyad's right to refuse participation and to withdraw at any time during the study period without affecting their routine clinical care.
4. The intervention will be provided by a team of highly trained professionals, who have extensive experience in caring for patients with moderate-severe dementia and their caregivers.
5. The procedures undertaken in the patient's home (which may include: clinical examination, recording of vital observations, blood draws, X rays, ultrasound) will be dictated only by the clinical needs identified using standardized assessments. The clinical team will record all encounters with the patient or caregiver in the secure

electronic medical record. Note - as of 3/19/2020 we will no longer be doing home visits as part of the intervention due to the risk of transmission of COVID-19 to a high risk population, with the exception of clinical emergencies that cannot be managed using telemedicine as previously documented.

6. Medications will be prescribed and de-prescribed according to need to treat clinical problems on the basis of clinicians' experience and in accordance with relevant guidelines. In all cases, medications will be prescribed by licensed providers, either the palliative care MD or the palliative care advanced practice nurse. Risks and benefits will be discussed in all cases of prescribing or de-prescribing a medication with the patient where they have capacity, or with their LAR when the patient lacks capacity. Additionally, the provider will communicate all medication changes to the patient's nominated physician.

7. All appropriate measures will be taken to ensure the secure transmission, storage and use of protected health information.

NOTE: The clinical intervention will provide an additional layer of support for patients with dementia and their caregivers and is designed to extend high quality palliative care to patients and their caregivers who, through functional and behavioral impairment, would not otherwise be able to access such services. Additionally, for patients in the control arm, the baseline interview will provide valuable information about the patient and caregiver needs which will be relayed to the patient's physician, potentially improving their care. In other words - what we are testing is a new, additional layer of support for individuals with profound needs, and adding more care to their care team - the drugs/ interventions/protocols that we are using are already well established best practice guidelines for the care of patients with advanced dementia.

## **9. Subjects - Participation**

### **Duration of an Individual Subjects Participation in the Study**

6 months

### **Duration Anticipated to Enroll All Study Subjects**

2 years

### **Estimated Date for the Investigators Within 3-5 years to Complete This Study**

### **Procedures for Subjects to Request Withdrawal**

At the time of enrollment, we will emphasize subjects' right to withdraw. If a subject/ their LAR wishes to withdraw, they will make contact with either the research staff or the Principal Investigator. When this happens, the research coordinator will complete a study termination form to indicate subject withdrawal from the study. We will record why the subject wished to withdraw (with their or LAR agreement) as this will provide additional data around the acceptability of the intervention. Where subjects/ LAR wish to withdraw from the study, we will request permission to collect information from their routine medical care (for patients only), as documented on the consent form.

### **Procedures for Investigator to Withdraw Subjects**

1. Death of patient (caregiver will be withdrawn)
2. No available caregiver
3. Transition to long term care (patients and caregivers)
4. Transition to skilled nursing facility for longer than 30 days (patients and caregivers)
5. Inpatient hospitalization for longer than 30 days (patients and caregivers)
6. Relocation of patient outside of Manhattan
7. Safety of clinical team cannot be assured
8. Study stopped
9. Principal Investigator deems it to be in the subject's best interest
10. The subject withdraws permission to use their PHI for research

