**Specify Other Setting of Human Research**

Patient home - we enroll subjects in their home as well as conducting follow up interviews in their home. This has been specified elsewhere in the previously approved protocol. This is because without home enrollments, many of the subjects would not be able to access the study.

Note - from 3/19/2020, we will no longer plan to conduct home enrollments, due to the risk of transmission to patients from COVID-19. Instead, we will transition to using an electronic consent protocol. Baseline and follow up interviews will be conducted telephonically in all cases.

**Total Number of Subjects Needed 250  
To Complete Study**

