#### **2. Control subjects**

While control subjects will not receive clinical care, research coordinators will undertake interviews with patients (or proxies) and caregivers at baseline. The results of these interviews will be relayed to the patient's nominated physician. These will serve to highlight previously unrecognized problems. Additionally, caregivers in the control arm will be offered coaching from a health coach on health improvement (e.g., dietary education, smoking cessation). The health coach will be certified in providing health education.

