### **Description of Procedures Being Performed**

#### **Intervention dyads**

For intervention dyads, the CHW, RN, and SW team conduct in-depth intake assessments that may include assessment of the following: disease stage (RN); physical, psychological and behavioral symptoms (RN); cognitive, functional and nutritional status (RN); medication reconciliation (RN); durable medical equipment needs (RN); dyad understanding of disease, goals of care, and advance directives (RN+SW); caregiver support network (SW); caregiver burden and unmet needs (SW); legal, financial and insurance needs (SW); spiritual concerns (SW). The CHWs accompany the RN and SW on initial visits to develop an understanding of the family and cultural context and their need for connections to community resources. The care team creates a comprehensive care plan to address the needs identified at the intake assessment. The care plan is implemented with the support of the CHWs, SW and RN and evaluated regularly. From 3/19/20 and due to the COVID-19 pandemic, all initial video visits and subsequent assessments will be conducted using video visit software. However, in the exceptional case that the patient has a clinical emergency that, according to the MD/NP cannot be managed using telemedicine and/or transfer to the hospital (e.g., uncontrolled agitation in a patient whose goals of care are to remain at home) we will consider the option of a home visit, after a thorough assessment and documentation in the clinical record of the risks and benefits, and guided by Institutional procedures for home visits in the context of the COVID-19 emergency which include strict adherence to infection control procedures. Note, to provide for this unlikely event, all team members have been trained in the use of personal protective equipment.

As a co-management model, the team works collaboratively with the PCP and existing in-home services such as home health aides or visiting nurse services with the goal to provide an added layer of support, rather than replace existing care.

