#### **Control dyads**

Dyads randomized to control will continue to receive care with their usual care providers. In addition, a copy of their baseline assessment will be uploaded into the EMR with the subject's consent, and the provider notified of this by email, with explicit notification of any areas for concern (i.e., uncontrolled symptoms). In addition, the caregiver-subject within control dyads will receive a health coach who will identify a physical health goal with the caregiver (e.g. weight reduction, smoking cessation) and work, through monthly visits, towards this goal. This control arm will assure balance between the groups in terms of "attention received" in a way that will not impact study outcomes.

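### Withdrawal for clinical-team safety in effect operates in the intervention arm only, and neither document keeps those dyads in follow-up or in the analysis

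*Protocol*

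**What the plan says.** Protocol section 9 (Procedures for Investigator to Withdraw Subjects) gives ten reasons. The seventh is "Safety of clinical team cannot be assured". It names no arm, trigger or threshold, and does not say whether outcomes are still collected afterwards. The shorter list in section 24 (Anticipated Circumstances of Subject Withdrawal) omits it.

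The protocol does not formally define the clinical team, but section 8 uses the term for the study's own caregivers to patients: "The clinical team caring for the patients in this study have extensive experience". For controls, section 10 says "While control subjects will not receive clinical care, research coordinators will undertake interviews", and section 12 says "Dyads randomized to control will continue to receive care with their usual care providers". Their other study contact is a health coach for the caregiver, who will "work, through monthly visits, towards this goal".

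From 3/19/20 intervention visits are by video or telephone. Section 12 allows a home visit in an exceptional emergency, with the example of "uncontrolled agitation in a patient whose goals of care are to remain at home". On outcome assessment, section 7 states: "Baseline and follow up interviews will be conducted telephonically in all cases". Section 12 gives the follow-up interviews to a research coordinator who does not know the assignment.

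Section 9 covers data after withdrawal only where the subject or representative asks to leave; permission is then sought to use the patient's routine records. The SAP plans a mixed linear model on baseline, 3-month and 6-month scores and gives no analysis set and no rule for withdrawn dyads.

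**The concern.** Two dyads posing the same hazard could be handled differently because of their allocation: one could be withdrawn because a study team is exposed to it, and the other would stay because no study team is involved. That is a post-randomization loss open to one arm only. The decision belongs to the investigator, and the protocol blinds only the follow-up interviewer.

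If the hazard is related to outcome, the arms are no longer comparable. A link is plausible: patients have advanced dementia, agitation and neuropsychiatric symptoms are measured, and the protocol's own example of a situation that could bring staff into the home is uncontrolled agitation. The co-primary symptom and quality-of-life scores and caregiver burden could all be affected.

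Utilization is exposed too. Section 20 captures encounters from enrollment to study termination, and SAP section 4 plans counts with no adjustment for time observed. If capture ends at withdrawal, one-arm truncation lowers that arm's admissions, hospital days and ED visits, and also its counted days out of hospital.

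**Working it through.** The documents give no withdrawal rate, SD, effect size or bias estimate, so there is no figure to reproduce. The first two steps set the text side by side; the other two are illustrations on stated assumptions.

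**1. Which arm.** Sections 8, 10 and 12 together place the clinical team in the intervention arm and leave controls with usual providers and a coach. That the reason applies to one arm is an inference, because the list carries no arm restriction, but it is the natural reading.

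**2. What happens to the dyad.** The list governs leaving the study, not only leaving the program. Continued record collection is provided for subject-requested withdrawal alone, and the SAP is silent.

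**3. Size.** Inputs from the protocol: 125 dyads, 1:1, so about 62 per arm. Assumptions: a normal outcome; a share p of the intervention arm withdrawn, being the worst on some criterion; and a correlation r between criterion and outcome of 0.5 to 1. The shift in that arm's raw mean, in SD units, is r × φ(z)/(1 − p), where z is the upper-p normal quantile. The standard error of the arm difference is √(2/62) = 0.180 SD.

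| p | Dyads (62p) | φ(z)/(1 − p) | Shift, r = 0.5 | Shift, r = 1 | In standard errors |
|---|---|---|---|---|---|
| 2% | 1.2 | 0.0484/0.98 = 0.049 | 0.025 | 0.049 | 0.14–0.27 |
| 5% | 3.1 | 0.1031/0.95 = 0.109 | 0.054 | 0.109 | 0.30–0.61 |
| 10% | 6.2 | 0.1755/0.90 = 0.195 | 0.097 | 0.195 | 0.54–1.08 |

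These are shifts in a raw mean, not the bias of the planned mixed model, which can recover part of the loss from earlier scores.

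**4. Direction.** A large simulation (1,000,000 per arm) assumed no treatment effect, a baseline-to-follow-up correlation of 0.5, and removal of the worst 5% from the intervention arm. Higher scores are worse, so a negative difference favors the intervention.

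| Basis for removal | Raw follow-up means | Completers' change from baseline | Baseline-adjusted |
|---|---|---|---|
| State at follow-up | −0.108 | −0.055 | −0.083 |
| Severity at baseline | −0.052 | +0.056 | +0.002 |

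The change-score results agree with the closed form: (1 − 0.5) × 0.109 = 0.054, negative in the first row and positive in the second. So removal that follows deterioration after baseline favors the intervention under all three analyses. Removal driven by baseline severity gives almost no bias after baseline adjustment, and the opposite sign for completers' change.

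**The case against.** A reader might infer that this reason strips the most disturbed patients from the intervention arm and so tilts the result in its favor. The documents do not support that. The reason is not tied to patient behavior; a hazard from the building, another household member or infection fits equally well. Nor is the sign fixed, as the second table shows.

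Frequency is the next objection, and it stands. With remote visits and home visits reserved for exceptional emergencies, the reason has little scope. Withdrawing 5–10% of the arm for team safety is hard to credit, and at about one dyad the worst case is roughly a quarter of a standard error. Emergency home visits and paramedic dispatch remain possible, so the scope is small but not nil.

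Three further points are fair. The agitation and neuropsychiatric inventories are collected but are not among the endpoints in section 3, so a link to the co-primary scores is an assumption. Considering a home visit for uncontrolled agitation does not contradict withdrawing a subject when safety cannot be secured. And section 23 refers to an analysis plan in a proposal not supplied here, which may say how withdrawn dyads are handled.

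Finally, other listed reasons, such as long-term care or a long hospital stay, probably remove more dyads, and they too lack a follow-up rule. That is true, but those reasons can arise in either arm. What remains particular to this one is that its trigger exists, in effect, in one arm.

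**Conclusion.** The point holds as a design weakness. It permits an avoidable, investigator-decided withdrawal in what is in effect one arm, with no stated follow-up or analysis as randomized. It can bias the comparison, but these documents settle neither how often it would occur nor which way it would act.

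The likely size is small: at most about 0.02–0.05 SD for one dyad and 0.05–0.11 SD for three, against a standard error of about 0.18 SD. Those figures rest on assumed withdrawal rates, a normal outcome and a criterion–outcome correlation of 0.5 to 1. The conclusion that the reason is confined to the intervention arm rests on how the protocol uses the term clinical team, which it never defines. The change is worth making because it is cheap, not because the bias is likely to be large.

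**What to change.** - Take team safety off the list of reasons for leaving the study. Describe it only as a possible reason for ending clinical-team contact; when that happens is for the sponsor to decide.
- State that the dyad stays in the trial: the 3- and 6-month telephone interviews, record abstraction and utilization capture continue as for controls. A research coordinator does the interviews, so a risk to the clinical team is no reason to lose a telephone interview.
- State in the SAP that these dyads are analyzed in their randomized arm, and report by arm how many had team contact ended for this reason.
- Reconcile the withdrawal lists in sections 9 and 24. Also reconcile section 7, which makes all interviews telephonic, with section 12 (All dyads - data collection), which still allows them in person.

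The cost is a short amendment and a few extra calls of about 30 minutes each. The downside is slight dilution of the estimated effect, because it will include intervention dyads whose team contact ended early.

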### **Participants Will Be Recruited**

Yes

### **Recruitment Method(s)**

Clinical Practice, Records (e.g. Medical, Employment, School), Information Letter/ Pamphlets, Physician Referral

### **How Participants Will Be Identified**

1. Patients will be identified either by physician referral or through a data warehouse query and subsequent chart screen.

#### **Data warehouse query**

Every quarter, we will obtain a cohort of patients from the Mount Sinai Data Warehouse who have a diagnosis of dementia (this is obtained either from their problem list or as a billing encounter). The problem list is contained within the patient's EMR and collated centrally by the data warehouse. The billing codes are diagnosis codes generated at the time of the clinical encounter by the treating provider and collated centrally.

We will then screen the charts to see whether these patients have evidence of moderate to severe dementia as one of the following:

- (i) Physician note of behavioral or psychological symptoms of dementia (i.e., agitation, anxiety, depression, irritability, apathy, elation, disinhibition, delusions, hallucinations, sleep disturbance)
- (ii) Psychotropic medication (antidepressant, anxiolytic, antipsychotics)
- (iii) Documented MMSE < 20
- (iv) Other evidence of advanced dementia: any from: needs assistance with dressing, bathing, toileting; urinary or fecal incontinence; weight loss; dysphagia/ aspiration; immobility; loss of ability to communicate.

The data collection sheets for the data warehouse and chart screening are contained in this application.

We will email these patients' physicians to introduce the study, confirm eligibility (moderate to severe dementia, available caregiver, resident in Manhattan outside of long term care, not receiving hospice). We will then ask the

physician to introduce the study to the patient and their caregiver, in the way they see fit, and if the patient and caregiver are interested in the study, we will contact the patient and caregiver to discuss.

#### Physician referral

We will outreach to physicians at targeted practices (Geriatrics, Primary Care, Internal Medicine) to inform them of the study and request that they refer dyads who may be interested. For these patients, we will confirm eligibility with the physician (moderate to severe dementia, available caregiver, residence in Manhattan outside of long term care, not receiving hospice) before meeting with the dyad.

Finally, we will distribute information to clinic physicians by hand.

2. Caregivers will be identified by the patient or their LAR at the time of introducing the study. It is highly likely that the patient's LAR and caregiver are the same.

Who Will Initially Approach Potential Participants	Member of Primary Care Team, Treating Physician, Clinic Personnel
---	---

#### How Research Will Be Introduced to Participants

In all cases, we will ask the patient's treating provider to introduce the study to the patient or their legally authorized representative and if they are interested, the study team will contact them by telephone.

#### How Participants Will Be Screened

Prior to contacting the dyad, the study team will ensure they meet inclusion criteria. Specifically, they will confirm with the physician that they have moderate-severe dementia, a caregiver who may be willing to enroll, are resident in Manhattan, outside of long term care and not receiving hospice.

When the research coordinator introduces the study to the dyad by telephone they will once again ensure they meet these criteria.

The RC will additionally confirm ahead of sending consent forms to the patient whether they have capacity (this will be documented by the patient's treating physician).

